3.3. Sample Size Considerations

The primary endpoint of this study is the proportion of participants with $\geq 25\%$ spleen volume reduction from baseline to Week 24 as measured by MRI (or CT scan in applicable participants). The primary endpoint will be analyzed by the CMH test stratified by baseline (or screening, if applicable) platelet count ($\geq 100 \times 10^9/L$ vs 50 to $< 100 \times 10^9/L$ inclusive) and DIPSS risk category (high vs intermediate-2 vs intermediate-1) at randomization. Assuming a 25% response rate for ruxolitinib + parsaclisib versus 5% for ruxolitinib + placebo, to achieve a 95% power to detect a statistically significant difference with a 2-sided Type 1 error of 5%, a sample size of 212 participants is required to be randomized equally between treatment groups.

For the key secondary endpoint of MFSAF TSS, assuming a response rate of 35% (25%) with ruxolitinib + parsaclisib for participants with normal (low) platelet counts and a response rate of 15% (10%) with ruxolitinib + placebo for participants with normal (low) platelet counts, a sample size of 212 will provide 81.3% power using the CMH test given a 2-sided Type 1 error of 5%.

A test for OS will be performed when 84 deaths are observed or the last participant achieved Week 24 assessments of spleen volume and MFSAF TSS, whichever is later, using the log-rank test at a 2-sided Type 1 error level of 0.05. The log-rank test will provide 80% power to detect an HR of 0.54 with 84 deaths. Assuming a median survival time of 3.7 years for ruxolitinib + placebo and an enrollment duration of 1 year, the expected total study duration is 4 years.

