Time to the first $\geq 25\%$ reduction in spleen volume	Inference: Log-rank test with stratification of baseline (or screening, if applicable) platelet count ($\geq 100 \times 10^9/L$ vs 50 to $< 100 \times 10^9/L$ inclusive) and DIPSS (high vs intermediate-2 vs intermediate-1) at randomization Estimation: Kaplan-Meier	ITT	P
Duration of maintenance of a $\geq 25\%$ reduction in spleen volume	Estimation: Kaplan-Meier	ITT with spleen response	P
Time to the first $\geq 50\%$ reduction in TSS as measured by the MFSAF v4.0 diary	Inference: Log-rank test with stratification of baseline (or screening, if applicable) platelet count ($\geq 100 \times 10^9/L$ vs 50 to $< 100 \times 10^9/L$ inclusive) and DIPSS (high vs intermediate-2 vs intermediate-1) at randomization Estimation: Kaplan-Meier	ITT	P

Due to the early termination of the study, only preplanned analyses will be performed. Supportive analyses will not be included. Time to event analyses with too few events observed at the time of study termination will not be conducted as well.

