9.1. General Considerations

The safety analyses, including frequency and severity of AEs and SAEs and mean change and percentage change in vital signs, ECGs, and lab parameters, will be summarized by treatment group in the safety population.

Summary tables may be replaced with listings when appropriate. For instance, an AE frequency table may be replaced with a listing if it only contains a few unique PTs reported on relatively few participants.

Safety analyses for treatment comparisons will exclude data collected after treatment crossover. Data post-treatment crossover will be analyzed separately and descriptively without any treatment comparisons. Day 1 of crossover will be used for the crossover participants in the crossover phase.

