9.2. Adverse Events

9.2.1. Adverse Event Definitions

A TEAE is any AE either reported for the first time or worsening of a pre-existing event after the first dose of study drug until 30 to 35 days after the last dose of study drug. Analysis of AEs (as discussed below) will be limited to TEAEs, but data listings will include all AEs regardless of their timing in relation to study drug administration. For purposes of analysis, all AEs will be considered TEAEs unless the AE can unequivocally be defined as not treatment-emergent.

Adverse events will be tabulated by MedDRA PT and SOC. Severity of AEs will be graded using the NCI CTCAE v5. The CTCAE reporting guidelines and grading details are available on the Cancer Therapy Evaluation Program website.

The subset of AEs considered by the investigator to be related to study drug will be considered to be treatment-related AEs. If the investigator does not specify the relationship of the AE to study

drug, the AE will be considered to be treatment-related. The incidence of AEs and treatment-related AEs will be tabulated. In addition, serious TEAEs will also be tabulated.

To summarize TEAEs using the life-table method, the time to first occurrence of a TEAE is defined as the interval between the date of first dose of study drug and the date of the first occurrence of a TEAE. Participants who have not experienced a TEAE at the time of analysis will be right-censored at the earlier of 30 to 35 days after the last dose of study drug and the date of last study visit through the end of safety follow-up. The effective sample size is defined as the number of participants at the beginning of interval minus half the participants censored in the interval. The conditional proportion is calculated as the number of first events divided by the effective sample size in the interval. If participants have missing or partial last dose dates of study drug, the partial or missing dates will be handled using the rules explained in Section 4.1.5. Any missing onset date of a TEAE will be handled according the following rules:

- If completely missing, then Day 1 will be used.
- If only the day is missing, then the first day of the month or Day 1, whichever is later, will be used.
- If both the month and day are missing, then 01 JAN of the year or Day 1, whichever is later, will be used.

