9.2.2. Adverse Events of Special Interest

The following TEAEs, regardless of seriousness, will be tabulated by MedDRA PT for the safety population for each treatment group.

- Colitis
- Diarrhea of Grade 2 or higher
- Rash of Grade 2 or higher
- Pneumonitis
- Dermatitis exfoliative
- Intestinal perforation
- Cytomegalovirus infection
- Herpes simplex infection, including oral herpes and genital herpes as AE terms
- Herpes (varicella) zoster virus infection, including herpes zoster, shingles, and VZV as AE terms
- Pneumocystis jirovecii infection
- ALT increased $\geq 5 \times$ ULN
- AST increased $\geq 5 \times$ ULN

Adverse events of special interest should be captured in the eCRF.

The time to onset of the first occurrence of each AESI will be analyzed using the KM method. Median time to onset of the first occurrence of each AESI will be estimated by the KM method. Participants with no AESI at the time of analysis will be censored at the time of analysis.

The longest duration of AESI will be analyzed using the KM method for participants in the safety population with at least 1 occurrence of the AESI. The median longest duration of each AESI will be estimated by the KM method. Participants whose AESI was not resolved at the time of analysis will be censored at the time of the analysis. Participants with nonserious TEAEs not resolved by 35 days after the end-of-treatment visit will be censored at 35 days after the end-of-treatment visit.

Two consecutive AESIs with different toxicity grades but with the start date of the later AESI overlapped with the end date of the previous AESI are considered as 1 AESI in calculating the duration of AESI.

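### SAP 9.2.2 censors participants without an AESI at the analysis date, so those lost to follow-up stay in the Kaplan-Meier risk set as event-free, unlike the rule in 9.2.1 for TEAEs (minor)

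*SAP*

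**What the plan says.** Section 9.2.2 introduces the AESI list as a subset of TEAEs: "The following TEAEs, regardless of seriousness, will be tabulated by MedDRA PT". It analyses time to first occurrence by Kaplan-Meier: "Median time to onset of the first occurrence of each AESI will be estimated by the KM method". The censoring rule for that analysis is one sentence: "Participants with no AESI at the time of analysis will be censored at the time of analysis". No earlier date is given for loss to follow-up, death, the end of the TEAE window or crossover.

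Section 9.2.1 limits a TEAE to onset or worsening after first dose "until 30 to 35 days after the last dose of study drug". For time to first TEAE, summarised by the life-table method, event-free participants are "right-censored at the earlier of 30 to 35 days after the last dose of study drug and the date of last study visit", with visits counted to the end of safety follow-up.

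On crossover, section 9.1 says "Safety analyses for treatment comparisons will exclude data collected after treatment crossover", and section 5.2 truncates between-group comparisons at early crossover unless otherwise specified. Neither section sets a censoring date for AESI onset.

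Appendix A, which Amendment 2 updated for the early termination, still lists the AESI onset analysis as Table 3.2.24.2 and Figure 4.3.1.

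**The concern.** A Kaplan-Meier risk set should contain only people in whom an event could still be recorded. Under 9.2.2 as written it also holds three groups in whom it could not, and they need separate treatment.

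- **Lost to follow-up while the TEAE window is open.** An AESI may have occurred, but nobody would know. Counting that time as event-free biases the onset curve downward whatever the target.
- **Past the TEAE window.** No later event can qualify as an AESI. Keeping these participants at risk treats the end of the window as a competing event.
- **Dead.** The same holds, with death as the competing event.

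For the last two groups the result can be a legitimate cumulative incidence. The SAP does not say that this is intended, and for the parent class of events 9.2.1 takes the opposite course and censors. At stake is how the onset curves read for the safety events the sponsor itself singled out.

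**Working it through.** The SAP states no AESI onset probability, discontinuation rate or loss rate, so it has no figure to reproduce. The check is an illustration on assumed constant monthly hazards, with exits independent of AESI risk.

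**Inputs.** AESI hazard l = 0.02 (assumed); loss hazard m = 0.01 or 0.02 (assumed); discontinuation hazard d (assumed); window after last dose w = 1 month (rounded from the 30 to 35 days in 9.2.1); horizon T = 12 months.

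**Censoring when observation ends (9.2.1 approach).** F = 1 − e^(−lT) = 1 − e^(−0.24) = 21.3%.

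**Loss only, censored at the analysis date (9.2.2 as written).** F* = l/(l+m) × (1 − e^(−(l+m)T)).
- m = 0.01 (1 − e^(−0.12) = 11% lost by month 12): 0.02/0.03 × (1 − e^(−0.36)) = 20.2%.
- m = 0.02 (1 − e^(−0.24) = 21% lost): 0.02/0.04 × (1 − e^(−0.48)) = 19.1%.

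The shortfall is about 1 to 2 points. With a rarer AESI at l = 0.005 the values are 5.5% and 5.2%, against 5.8%.

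**Discontinuation only.** F* = (1 − e^(−lw)) + l·e^(dw)/(l+d) × (e^(−(l+d)w) − e^(−(l+d)T)). For d = 0.02, 0.04 and 0.06 this gives 19.4%, 17.8% and 16.3%. The gap from 21.3% is a change of target, not a bias.

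**Loss judged against the competing-risk target.** With d = 0.04 the correct cumulative incidence is 17.8%. Adding loss at 1% or 2% per month, 9.2.2 gives 16.9% or 16.0%. The shortfall is again 1 to 2 points, so the loss error remains whichever target is meant.

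**Death only, at the SAP's design values.** Section 3.3 has "Assuming a median survival time of 3.7 years for ruxolitinib + placebo" and a hazard ratio of 0.54. The monthly hazards are ln 2/44.4 = 0.0156 and 0.54 × 0.0156 = 0.0084. Using these as m, with the window taken as open until death, 9.2.2 gives 19.5% on placebo and 20.3% on parsaclisib at equal AESI hazards. This too is a change of target.

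**Median onset.** At l = 0.02 the 9.2.1 median is ln 2/0.02 = 34.7 months, beyond an assumed follow-up of 18 to 30 months, and 9.2.2 can only lengthen it. At l = 0.05 it is 13.9 months under 9.2.1. Under 9.2.2 it is 15.3 or 17.2 months with 1% or 2% per month loss, and 16.6 or 22.4 months with 2% or 4% per month discontinuation.

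**Cross-check by simulation.** With 106 per arm, a true one-year incidence of 20% and 30% leaving observation within the year, Kaplan-Meier averaged 16.8% with leavers kept at risk and 19.9% when they were censored on leaving. The loss formula gives 16.9% for the first.

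**The case against.** The best defence is that the sentence in 9.2.2 is shorthand. The section gives no time origin for AESI onset, so it already leans on 9.2.1, and Table 3.2.24.2 is marked as a standard table whose specification is not shown. That is possible but not decisive. The 9.2.1 rule is introduced for the life-table method, and no text extends it to AESI onset. Elsewhere the SAP writes an observation-based date when it wants one: last scan in 7.4.1.1, last known alive in 7.4.3, and a 35-day limit for unresolved nonserious events in the AESI duration paragraph of 9.2.2 itself.

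Several points on size do stand:

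- The part that is wrong under any target covers only people lost on drug or within about a month of stopping. The SAP supports no rate for this.
- At the planned 106 per arm the standard error of a 20% proportion is √(0.2 × 0.8/106) = 3.9 points, so the assumed bias is roughly 0.3 to 0.6 of a standard error. The trial also stopped early.
- The median, the only onset summary that 9.2.2 and 9.2.3 name, moves only for a frequent AESI. A rate of 5% per month means 1 − e^(−0.6) = 45% affected within a year.
- Sparse outputs may never be produced. Section 9.1 allows listings in place of tables, and 9.2.3 does so where 10 or fewer participants appear. Section 5.3 adds "Time to event analyses with too few events observed at the time of study termination will not be conducted as well", though it concerns the primary and secondary endpoints and may not reach safety.

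A reader might also infer that Table 3.2.22 (life table) and Table 3.2.24.2 (Kaplan-Meier) will visibly contradict each other for a single-term AESI. The SAP does not establish this. Section 9.2.1 defines the life-table output as a conditional proportion per interval, so the two tables could differ even with identical censoring dates.

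**Conclusion.** The point holds and is minor. Sections 9.2.1 and 9.2.2 give different censoring rules for events of the same class. Read literally, 9.2.2 counts unobserved time after loss to follow-up as event-free and understates AESI onset risk. The size is about 1 to 2 points at 12 months if the AESI rate is 2% per month and loss is 1% to 2% per month. All these rates are assumed, and the comparison takes exits to be independent of AESI risk.

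A reader might go further and call it an error that participants who have died or passed the window stay at risk, or cite the larger discontinuation and death figures as bias. The SAP does not support that. Those figures describe a cumulative incidence with competing exits, which is a valid quantity. The fault is that the SAP neither names it nor reconciles it with 9.2.1.

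The effect is confined to Table 3.2.24.2 and Figure 4.3.1. No hypothesis test, futility rule or crude AESI count (Table 3.2.24.1) depends on it.

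**What to change.** Replace the censoring sentence in 9.2.2 so that participants with no AESI are censored at the earliest of:

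- the end of the TEAE window after last dose;
- the last study visit through safety follow-up;
- death;
- the data cutoff;
- crossover, consistent with 5.2 and 9.1.

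Fix the end of the window at a single day and use it in both 9.2.1 and 9.2.2. The present range of 30 to 35 days cannot be programmed as a date, and the choice of day is the sponsor's. Add a sentence that the curve describes onset while under observation on treatment, and that it relies on exits being unrelated to AESI risk.

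If a cumulative incidence is preferred, name discontinuation and death as competing events, use a competing-risk estimator, and still censor loss to follow-up and crossover when they occur.

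The cost is a few lines of SAP text and one derived date, with no new data.

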9.2.3. Adverse Event Summaries

An overall summary of AEs by treatment group will include the following:

- Number (%) of participants who had any TEAEs
- Number (%) of participants who had any serious TEAEs
- Number (%) of participants who had any Grade 3 or higher TEAEs
- Number (%) of participants who had any TEAEs related to parsaclisib
- Number (%) of participants who had any TEAEs related to ruxolitinib
- Number (%) of participants who had any TEAEs related to parsaclisib or ruxolitinib
- Number (%) of participants who temporarily interrupted parsaclisib because of TEAEs
- Number (%) of participants who temporarily interrupted ruxolitinib because of TEAEs
- Number (%) of participants who permanently discontinued parsaclisib because of TEAEs
- Number (%) of participants who permanently discontinued ruxolitinib because of TEAEs
- Number (%) of participants who had parsaclisib dose reductions because of TEAEs
- Number (%) of participants who had ruxolitinib dose reductions because of TEAEs
- Number (%) of participants who had any fatal TEAEs

The following summaries will be produced by MedDRA term (if 10 or fewer participants appear in a table, a listing may be appropriate):

- Summary of TEAEs by MedDRA SOC and PT
- Summary of TEAEs by MedDRA PT in decreasing order of frequency
- Summary of TEAEs by MedDRA SOC, PT, and CTCAE grade category
- Summary of Grade 3 or higher TEAEs by MedDRA SOC and PT
- Summary of Grade 3 or higher TEAEs by MedDRA PT in decreasing order of frequency
- Summary of serious TEAEs by MedDRA SOC and PT
- Summary of serious TEAEs by MedDRA PT in decreasing order of frequency
- Summary of parsaclisib/placebo treatment-related TEAEs by MedDRA SOC and PT
- Summary of ruxolitinib treatment-related TEAEs by MedDRA SOC and PT
- Summary of parsaclisib/placebo/ruxolitinib treatment-related TEAEs by MedDRA SOC and PT
- Summary of parsaclisib/placebo treatment-related TEAEs by MedDRA PT in decreasing order of frequency
- Summary of ruxolitinib treatment-related TEAEs by MedDRA PT in decreasing order of frequency
- Summary of parsaclisib/placebo treatment-related TEAEs by MedDRA SOC, PT, and CTCAE grade category
- Summary of ruxolitinib treatment-related TEAEs by MedDRA SOC, PT, and CTCAE grade category
- Summary of Grade 3 or higher parsaclisib/placebo treatment-related TEAEs by MedDRA SOC and PT
- Summary of Grade 3 or higher ruxolitinib treatment-related TEAEs by MedDRA SOC and PT
- Summary of parsaclisib/placebo treatment-related serious TEAEs by MedDRA SOC and PT
- Summary of ruxolitinib treatment-related serious TEAEs by MedDRA SOC and PT
- Summary of TEAEs with a fatal outcome by MedDRA SOC and PT
- Summary of TEAEs leading to parsaclisib/placebo dose reduction by MedDRA SOC and PT
- Summary of TEAEs leading to ruxolitinib dose reduction by MedDRA SOC and PT
- Summary of TEAEs leading to parsaclisib/placebo dose interruption by MedDRA SOC and PT

- Summary of TEAEs leading to ruxolitinib dose interruption by MedDRA SOC and PT
- Summary of TEAEs leading to discontinuation of parsaclisib/placebo by MedDRA SOC and PT
- Summary of TEAEs leading to discontinuation of ruxolitinib by MedDRA SOC and PT
- Summary of TEAEs by MedDRA PT: life-table method
- Summary of TEAEs by MedDRA SOC and PT: life-table method
- Summary of treatment-emergent AESIs by MedDRA PT
- Median time to the first onset of treatment-emergent AESIs by MedDRA PT
- Median longest duration of treatment-emergent AESIs by MedDRA PT

9.3. Clinical Laboratory Tests

9.3.1. Laboratory Value Definitions

Laboratory values and change from baseline values will be summarized descriptively by visit. Baseline will be determined according to Section 4.1.4. If there are multiple values that meet the criteria for baseline, the value from the central laboratory has priority over the value from the local laboratory. Thereafter, additional rules may be provided after consultation with the medical monitor to delineate which value will be defined as baseline.

Laboratory test values will be assessed for severity based on the numerical component of CTCAE v5.

9.3.2. Laboratory Value Summaries

All test results and associated normal ranges from central laboratories will be reported in SI units. Any laboratory test results and associated normal ranges from local laboratories will be converted to SI units.

When there are multiple nonmissing laboratory values for a participant's particular test at a scheduled visit, central laboratory values have higher priority over local laboratory values. If a tie still exists, the laboratory value with the smallest laboratory sequence number will be used in by-visit summaries.

Numeric laboratory values will be summarized descriptively in SI units, and non-numeric test values will be tabulated when necessary. In addition, line plots will be provided for HGB, platelet counts, leukocytes, and neutrophils.

A table for the number of participants with abnormal ALT, AST, bilirubin, and creatinine will be tabulated by treatment group.

For test results that will be summarized with available normal ranges, the number and percentage of participants with laboratory values being low (but never high), normal, high (but never low), and both low and high will be calculated for each test.

Severity grades will be assigned to laboratory test values based on the numerical component of CTCAE v5. Shift tables will be presented showing change in CTCAE grade from baseline to worst grade postbaseline. Separate summaries for abnormally high and abnormally low laboratory values will be provided when the laboratory parameter has both high and low grading criteria. The denominator for the percentage calculation will be the number of participants in the baseline category. The number of participants who experienced worsening of laboratory abnormalities will be summarized by maximum severity.

In cases where differentials of hematology parameters are obtained without corresponding absolute count data, efforts will be made to investigate if the conversion to an absolute value will lead to additional abnormalities. This will be discussed with the clinical team regarding appropriate documentation and action.

9.3.3. Potential Hy's Law Events

Participants with elevated ALT or AST $> 3 \times$ ULN range and alkaline phosphatase $< 2 \times$ ULN range accompanied by total bilirubin $> 2 \times$ ULN range at the same visit will be listed by treatment group.

9.4. Vital Signs

Values at each scheduled visit, change, and percentage change from baseline for vital signs, including systolic blood pressure, diastolic blood pressure, pulse, temperature, respiratory rate, and weight will be summarized descriptively.

Normal ranges for vital signs are defined in [Table 5](#). For participants exhibiting vital sign abnormalities, the abnormal values will be listed along with their assigned treatment group. Alert vital signs are defined as an absolute value outside the defined normal range and percentage change greater than 25%. Note that the definition of alert vital signs does not apply for body temperature and weight. The abnormal values for participants exhibiting alert vital sign abnormalities will be listed.

Table 5: Normal Ranges for Vital Sign Values

Parameter	High Threshold	Low Threshold
Systolic blood pressure	≤ 155 mmHg	≥ 85 mmHg
Diastolic blood pressure	≤ 100 mmHg	≥ 40 mmHg
Pulse	≤ 100 bpm	≥ 45 bpm
Temperature	$\leq 38^{\circ}\text{C}$	$\geq 35.5^{\circ}\text{C}$
Respiratory rate	≤ 24 breaths/min	≥ 8 breaths/min

9.5. Electrocardiograms

Twelve-lead ECGs including PR, QT, QRS, RR, QTc, QTcB, and QTcF intervals will be obtained for each participant during the study. Values at each scheduled visit, change, and percentage change from baseline will be summarized for each ECG parameter. Baseline will be determined as the average of all nonmissing values before the first administration of parsaclisib, placebo, or ruxolitinib.

Normal ranges for ECG values are defined in **Table 6**. Electrocardiogram values will also be considered abnormal if the absolute percentage change from baseline is more than 25% (30% for QRS interval). Participants exhibiting ECG abnormalities will be listed with study visit and assigned treatment group. Abnormal values for participants with alert ECG values, defined as both the absolute value and the percentage change from baseline being outside normal ranges, will be identified and listed. Outliers of QT and QTc values, defined as absolute values > 500 milliseconds, ≥ 480 milliseconds, and > 450 milliseconds for each parameter or change from baseline > 30 milliseconds and > 60 milliseconds for each parameter, will be summarized.

Table 6: Normal Ranges for Electrocardiogram Intervals

Parameter	High Threshold	Low Threshold
PR	≤ 220 ms	≥ 75 ms
QT	≤ 500 ms	≥ 300 ms
QRS	≤ 120 ms	≥ 50 ms
QTc	≤ 450 ms	≥ 295 ms
RR	≤ 1330 ms	≥ 600 ms

